8.1.1 Part A SAD, Healthy Volunteers

Subjects will be admitted to the clinical research unit (CRU) on the day prior to (first) drug administration (Day -1). Following drug administration of a single dose of BMS-986251 on Day 1, they will remain in the CRU for close observation until discharge from the CRU on Day 7 (144 hours post-dose). Subjects will return for ambulatory assessments on Days 9 and 11, including follow-up assessments on Day 11.

Subjects enrolled in the BA/FE cohort will return to the CRU for a 2nd and 3rd study period. Washout between single dose administrations will be at least 2 weeks, based on an anticipated terminal half-life of BMS-986251 of approximately 40 hours. The design of the 2nd and 3rd study period is the same as the first period, with a mandatory in-clinic stay from Day -1 to Day 7 and ambulatory visits on Days 9 and 11. Subjects will be dosed on Day 1 of each period. Follow-up assessments will be performed on Day 11 of Period 3 only; on Day 11 of Period 1 and 2 limited assessments including blood sampling for PK and PD (PD only in Period 1) will be performed. Please refer to the procedural outline in Table 1 to see which assessments are to be performed at each visit.

The planned single dose treatments are provided in Table 6. Eight healthy subjects will be assigned to each of 6 planned SAD cohorts and the BA/FE cohort. Subjects will be randomized within each of the SAD cohorts to receive a single oral dose of BMS-986251 or a matched placebo in a ratio of 3:1. All subjects in the BA/FE cohort will receive BMS-986251. In the first SAD cohort, sentinel dosing will be employed (see Section 8.1).

Within each cohort, safety, tolerability, PK, and PD assessments will be performed at predefined time points. Following completion of each dose cohort there will be a review of blinded study data prior to dose escalation by the Sponsor's dose escalation review group. This group will include the Investigator, PRA Medical Monitor, the BMS Study Director, and additional personnel as deemed necessary by the Sponsor (such as a pharmacokineticist). SAD dose escalation decisions will be based on the safety, tolerability and PK results of the ongoing cohort up to and including Day 7, and on the PD results up to and including Day 5. Medication administration in the next dose cohort will not start until at least 6 subjects have been dosed in the previous dose cohort and the data have been reviewed. The dose escalation

review group will determine whether escalation to the next dose level will occur or whether dose-stopping criteria (presented in Section 8.3.5.5) have been met.

As new safety and/or PK data become available, the dose-escalation scheme may change. Subjects in subsequent dose cohorts may not receive a subsequent higher dose as outlined, but may instead be administered a lower dose than originally planned, repeat a lower dose level, or repeat the same dose of the study drug.

Table 6 IM024 005; Part A Dose Cohorts

Cohort	Number of Subjects (Active / Placebo)	Period	Dose of BMS-986251	Fasted / Fed	Formulation
A1	1 / 1 (sentinel group)	1	2 mg	Fasted	Oral solution
	5 / 1	1	2 mg	Fasted	Oral solution
A2	6 / 2	1	6 mg	Fasted	Oral solution
A3	6 / 2	1	15 mg	Fasted	Oral solution
A4	6 / 2	1	30 mg	Fasted	Oral solution
A5	6 / 2	1	60 mg	Fasted	Oral solution
A6	6 / 2	1	120 mg	Fasted	Oral solution
A7 (BA/FE)	8	1	tbd	Fasted	Oral solution
		2	tbd	Fasted	Oral suspension (under development)
		3	tbd	Fed	Oral suspension (under development)

BA = bioavailability; FE = food effect; tbd = to be determined
Doses may be adjusted based on data obtained in previous cohorts.

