8.1.2 Part B MAD, Healthy Volunteers

Part B will be initiated after thorough review of safety, tolerability, PK and PD data from at least the SAD Cohorts A1 up to A4 from Part A.

Subjects enrolled in Part B of the study will be admitted to the CRU on the day prior to first drug administration (Day -1). Subjects will be dosed with BMS-986251 on Days 1-14. During treatment they will remain in the CRU for close observation. Subjects will be discharged on Day 16 (48 hours after the last dose). Subjects will return for ambulatory assessments on Days 18, 20, and 24, including follow-up assessments on Day 24.

The planned multiple dose treatments are provided in Table 7. Eight healthy subjects will be assigned to each of 4 planned dose cohorts. Subjects will be randomized within each dose cohort to receive multiple oral doses of BMS-986251 or a matched placebo in a ratio of 3:1.

Within each cohort, safety, tolerability, PK, and PD assessments will be performed at predefined time points. Following completion of dosing for each MAD dose cohort there will be a short period to review the data and inform dose escalation by the Sponsor's dose escalation review group. MAD dose escalation decisions will be based on the blinded safety, tolerability, PK and PD of the ongoing cohort up to and including Day 14. Ongoing review of SAD safety, tolerability, PK and PD data will also be considered for dose-escalation in

Part B. The dose escalation review group will determine whether escalation to the next dose level will occur or whether dose-stopping criteria (presented in Section 8.3.5.5) have been met.

As new safety and/or PK data become available, the dose-escalation scheme may change. Subjects in subsequent dose cohorts may not receive a subsequent higher dose as outlined, but may instead be administered a lower dose than originally planned, repeat a lower dose level, or repeat the same dose of the study drug.

Table 7 IM024 005; Part B Dose Cohorts

Cohort	Subjects (Active / Placebo)	Dose of BMS-986251	Duration	Fasted/Fed	Formulation
B1	6 / 2	6 mg QD	14 days	Fasted	Oral solution
B2	6 / 2	tbd QD	14 days	Fasted	Oral solution
B3	6 / 2	tbd QD	14 days	Fasted	Oral solution
B4	6 / 2	60 mg QD	14 days	Fasted	Oral solution

QD = once daily; tbd = to be determined upon reviewed data
Doses may be adjusted based on data obtained in previous cohorts.

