8.3.5.5 Stopping Rules for Part A and Part B

In the assessment whether AE related criteria for halting or stopping are met, special attention will be paid to any AE that is classed by the investigator as:

- A sign or symptom of bacterial, fungal or viral infection.
- An intestinal disorder.
- A hematological abnormality.

Dosing within a dose cohort will be stopped and further dosing will be halted until unblinded safety information (of the subject with the event) can be reviewed in case of one or more of the following occurring at any time during the observation period in the ongoing cohort:

1. A clinically significant AE that in the opinion of the Investigator, BMS Study Director and PRA Medical Monitor, indicates that the limits of safety and tolerability have been met, and precludes further safe dosing of subjects.
2. Two or more subjects with a severe or serious AE considered to be related to the study drug.
3. Two or more subjects with a serious infection event or 1 subject with opportunistic infection requiring systemic therapy (assessed as related to study drug).
4. Two or more subjects with liver function test elevations (confirmed by repeat) in the absence of an alternative explanation, including:
 - aspartate aminotransferase (AST) or alanine aminotransferase (ALT) > 5 x upper limit of normal (ULN)
 - AST or ALT > 3 x ULN with symptoms consistent with hepatic inflammation
5. One or more subjects with liver function test elevations (confirmed by repeat) consistent with drug-induced liver injury, in the absence of an alternative explanation, including:
 - AST or ALT > 3 x ULN and total bilirubin > 2 x ULN
6. Two or more subjects have a greater than 60 msec increase in QTcF from the baseline value or a QTcF of > 500 msec (confirmed by repeat ECG).

Pending review of all pertinent information collected to date, one of the following decisions may be made:

- To continue dosing the remaining subjects of the cohort as planned, or
- To reduce the dose and continue dosing the remaining subjects of the cohort at the modified dose level (or placebo), or
- To terminate further dosing in the ongoing cohort.

In case of one or more occurrences as listed above, **dose escalation** will be halted until unblinded safety information for the subject(s) in the last completed cohort and with the event(s) can be reviewed. Pending review of all pertinent information collected to date, one of the following decisions may be made:

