Within each cohort, safety, PK, and PD assessments will be performed. The bioanalytical personnel responsible for performing the analyses of the PK samples will be unblinded throughout the study to prevent unnecessary analysis of placebo samples. Following completion of each dose panel, there will be a review period between panels, during which all available safety, tolerability, PK, and PD data (as applicable) will be reviewed by the Sponsor's dose escalation review group. Limited designated staff of BMS and/or PRA can be unblinded at this time to prepare preliminary summaries of PK, PD and safety data. These summaries will not reveal individual subjects' treatment assignments and will include summaries and figures of mean data (as applicable). The Sponsor's dose escalation review group will review the data and will determine whether escalation to the next dose level will occur, or whether dose-stopping criteria have been met. The pharmacist at the site and/or designate will be unblinded to the randomized treatment assignments in order to dispense treatment from bulk supplies, as needed. Except as noted above, other members of BMS Research and Development and PRA will remain blinded.

Randomization schedules will be shipped directly to a pharmacist or other individual(s) who will be responsible for the dispensing of blinded study drug. This (these) individual(s) will be unblinded to study drug identification but will not be involved in any other aspect of study conduct. The randomization schedules will be maintained in a secure location with access limited to authorized personnel.

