9.4.5 Interim Analysis

Dose escalation reports will be prepared after each cohort in Parts A and B after completion of each cohort. Safety and preliminary PK and/or PD data from Parts A and B will be summarized as an interim report prior to initiation of Part C. The report will be submitted to the relevant health authorities.

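### Does Protocol 8.1.1 describe the Part A escalation gate in conflicting ways, and does its floor of 6 dosed subjects weaken the two-subject stopping rules?

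*Protocol*

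**What the plan says.** Protocol 8.1.1 makes three statements about moving from one Part A cohort to the next.

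- **When the review happens:** "Following completion of each dose cohort there will be a review of blinded study data prior to dose escalation".
- **What data it uses:** safety, tolerability and PK "results of the ongoing cohort up to and including Day 7", and PD to Day 5. Ambulatory visits run on to Day 11.
- **How many subjects:** "Medication administration in the next dose cohort will not start until at least 6 subjects have been dosed in the previous dose cohort". The same sentence also requires that the data have been reviewed.

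Two other sections describe the same step. Section 8.4.3.2 says "Following completion of each dose panel, there will be a review period between panels", and Section 9.4.5 says "Dose escalation reports will be prepared after each cohort in Parts A and B after completion of each cohort". For Part B, Section 8.1.2 is more specific: "Following completion of dosing for each MAD dose cohort there will be a short period to review the data".

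Among the stopping rules in Section 8.3.5.5, rules 2, 4 and 6 and the first half of rule 3 need at least two subjects. Rule 2 reads "Two or more subjects with a severe or serious AE considered to be related to the study drug". Rules 1 and 5, and the opportunistic-infection half of rule 3, have no two-subject threshold.

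**The concern.** A cohort at Day 7, or one with 6 of its 8 subjects dosed, is not complete in the ordinary sense when visits run to Day 11. Section 8.1.1 does not define completion for Part A, and Part B's narrower phrase about dosing is not used there. The floor could therefore mean either of two things:

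1. It covers a cohort that ends with fewer than 8 subjects.
2. It lets the next dose level start while 2 of the 8 are still to be dosed.

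The floor also counts dosed subjects, whereas the detection probability in Section 9.1 is for 6 subjects on BMS-986251. With 2 placebo subjects per cohort, 6 dosed could mean 4, 5 or 6 on active drug. If the gate opened at 4 active, a rule that needs two affected subjects would be less likely to be met before the next dose level began. The gate governs every step from A1 to A6, so a real defect would concern subject safety.

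**Working it through.** **1. The plan's own figure.** Section 9.1 (repeated in SAP 6.1) claims about 80% probability of at least one occurrence at 24% incidence with 6 on active drug. The formula is 1 − (1 − p)^n. With p = 0.24 and n = 6, 1 − 0.76^6 = 1 − 0.193 = 0.807. The figure is reproduced.

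**2. The passages side by side.**

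| Place | What it fixes |
|---|---|
| 8.1, overall design | Part A cohorts are sequential |
| 8.1.1, first statement | Trigger: review follows the cohort |
| 8.1.1, second statement | Data cut: Day 7, PD Day 5 |
| 8.1.1, third statement | Minimum: at least 6 dosed, and data reviewed |
| 8.3.5.5 | An escalation halt refers to the most recent completed cohort |
| 8.4.3.2 | Review falls between panels, after each is completed |
| 9.4.5 | A report follows each completed cohort |

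The three statements in 8.1.1 answer different questions, so all can hold at once. Calling the cohort ongoing at Day 7 fits visits that continue to Day 11. Section 8.1.2 does the same for Part B: data to Day 14, visits to Day 24. Reading 1 fits every row. Reading 2 sits badly with sequential cohorts and with a review placed between completed panels.

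**3. Active subjects among 6 dosed.** Inputs: 6 active and 2 placebo (Section 8.1). Assumption: dosing order is random within the cohort. There are C(8,6) = 28 ways to choose the 6.

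- 4 active: C(6,4) × C(2,2) / 28 = 15/28 = 53.6%
- 5 active: C(6,5) × C(2,1) / 28 = 12/28 = 42.9%
- 6 active: 1/28 = 3.6%

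In A1 the sentinel pair is fixed at one of each, so the other 4 come from 5 active and 1 placebo: 4 active in total 10/15 = 66.7%, 5 active 5/15 = 33.3%.

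**4. Chance of two or more affected active subjects.** P = 1 − (1 − p)^n − n p (1 − p)^(n−1), with independent events on active drug only. For p = 0.24:

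- n = 4: 1 − 0.3336 − 0.4214 = 24.5%
- n = 5: 1 − 0.2536 − 0.4003 = 34.6%
- n = 6: 1 − 0.1927 − 0.3651 = 44.2%

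The average at 6 dosed, outside A1, is (15 × 0.2450 + 12 × 0.3461 + 1 × 0.4422) / 28 = 29.5%. That is 14.7 percentage points below the value with 6 active.

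**5. Sensitivity to incidence.** The 24% in Section 9.1 is a benchmark for any adverse event. The two-subject rules concern related severe or serious events, serious infections, marked liver test elevations and large QTcF changes. The documents give no incidence for these, so a range is assumed.

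| Assumed incidence | 4 active | 6 active |
|---|---|---|
| 5% | 1.4% | 3.3% |
| 10% | 5.2% | 11.4% |
| 24% | 24.5% | 44.2% |
| 50% | 68.8% | 89.1% |

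At 5% the two counts differ by 1.9 points, and a two-subject rule is rarely met with either.

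**6. What happened.** SAP 7.1 reports 8 dosed in each of A1 to A4, so no cohort that led to an escalation ended short. A5 had 4 dosed when the study was terminated for non-clinical findings (SAP 3.0), and A6 was not conducted. These totals cannot show when the last two subjects of a cohort were dosed relative to the next cohort, but nothing in the documents suggests an overlap.

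**The case for a change.** The best case for a change is that the number 6 has two meanings. In Section 9.1 it is the number on active drug, and it underlies the claim that the cohort size is sufficient. In Section 8.1.1 it counts dosed subjects in either arm. Where the split mattered elsewhere, as in the A1 sentinel pair, the protocol stated it. Replacement under Section 8.3.5.4 is optional, so it does not guarantee 6 on active drug. Clearer wording would cost little, and Section 8.4.3.2 already allows that "Limited designated staff of BMS and/or PRA can be unblinded at this time to prepare preliminary summaries of PK, PD and safety data", so an active count could be confirmed without unblinding the review group.

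Part of this stands. Completion is undefined for Part A, the scope of the floor is unstated, and 6 dosed does not guarantee 6 active.

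The rest does not amount to an error. The floor plainly counts dosed subjects, which suits a blinded review. Counting only active subjects would be a different design choice. The stopping rules count affected subjects whatever their arm, so the active number changes how likely they are to be met but not what they say. They also apply throughout the observation period of the ongoing cohort and do not lapse at the review. Section 8.3.5.5 lets the sponsor and investigator halt on trends within or across panels, and a triggered review looks at all safety data available in the study.

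**Conclusion.** No change follows. The statements in Section 8.1.1 are compatible, and Sections 8.1, 8.3.5.5, 8.4.3.2 and 9.4.5 favour reading the floor as cover for a cohort that ends short. What remains is missing detail, which the dose escalation review group can settle from its knowledge of who has been dosed and for how long. Following the text as written is not shown to give a wrong decision. Asking the sponsor to define the terms would not by itself improve any decision, and the choice of rule is the sponsor's.

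The largest effect that can be put on the gap is 24.5% against 44.2% at 24% incidence. It requires exactly 6 of 8 dosed with 4 of them active, events independent and confined to active drug, and an any-event benchmark applied to much more severe events. At 5% incidence it shrinks to 1.4% against 3.3%. The documents give no probability for stopping at 6 of 8. The study ended on June 25, 2018, so new wording could affect no escalation in it. The 80% figure in Section 9.1 and SAP 6.1 is correct for 6 on active drug and stands.

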8.1.2 Part B MAD, Healthy Volunteers

Part B will be initiated after thorough review of safety, tolerability, PK and PD data from at least the SAD Cohorts A1 up to A4 from Part A.

Subjects enrolled in Part B of the study will be admitted to the CRU on the day prior to first drug administration (Day -1). Subjects will be dosed with BMS-986251 on Days 1-14. During treatment they will remain in the CRU for close observation. Subjects will be discharged on Day 16 (48 hours after the last dose). Subjects will return for ambulatory assessments on Days 18, 20, and 24, including follow-up assessments on Day 24.

The planned multiple dose treatments are provided in Table 7. Eight healthy subjects will be assigned to each of 4 planned dose cohorts. Subjects will be randomized within each dose cohort to receive multiple oral doses of BMS-986251 or a matched placebo in a ratio of 3:1.

Within each cohort, safety, tolerability, PK, and PD assessments will be performed at predefined time points. Following completion of dosing for each MAD dose cohort there will be a short period to review the data and inform dose escalation by the Sponsor's dose escalation review group. MAD dose escalation decisions will be based on the blinded safety, tolerability, PK and PD of the ongoing cohort up to and including Day 14. Ongoing review of SAD safety, tolerability, PK and PD data will also be considered for dose-escalation in

Part B. The dose escalation review group will determine whether escalation to the next dose level will occur or whether dose-stopping criteria (presented in Section 8.3.5.5) have been met.

As new safety and/or PK data become available, the dose-escalation scheme may change. Subjects in subsequent dose cohorts may not receive a subsequent higher dose as outlined, but may instead be administered a lower dose than originally planned, repeat a lower dose level, or repeat the same dose of the study drug.

Table 7 IM024 005; Part B Dose Cohorts

Cohort	Subjects (Active / Placebo)	Dose of BMS-986251	Duration	Fasted/Fed	Formulation
B1	6 / 2	6 mg QD	14 days	Fasted	Oral solution
B2	6 / 2	tbd QD	14 days	Fasted	Oral solution
B3	6 / 2	tbd QD	14 days	Fasted	Oral solution
B4	6 / 2	60 mg QD	14 days	Fasted	Oral solution

QD = once daily; tbd = to be determined upon reviewed data
Doses may be adjusted based on data obtained in previous cohorts.

8.1.3 Part C, Multiple Dose in Psoriasis Patients

Part C will be initiated after thorough review of safety, tolerability, PK and PD data (as available) from Part A and Part B, and after verification that administration of BMS-986251 is safe and tolerable enough to administer in psoriasis patients.

In Part C, a total of 15 patients with moderate-to-severe psoriasis will be enrolled in 2 sub-cohorts: 1 sub-cohort with intensive PK sampling and 1 sub-cohort with sparse PK sampling.

At least 6 patients will be enrolled in the sub-cohort with intensive PK sampling. The patients enrolled in this cohort will be admitted to the CRU on the day prior to first drug administration (Day -1). Patients will be dosed with the first dose of BMS-986251 on Day 1 and will be discharged on Day 2 after intake of the 2nd dose. Between Day 3 and Day 12, the patients will take the medication once daily (QD) at home, except on Day 7. Treatment compliance information will be collected while subject is dosing at-home via dosing diaries. Patients will return to the CRU for an ambulatory visit on Day 7 and will be instructed not to take their morning dose at home, but instead bring their study drug and dosing diaries to the CRU for administration following pre-dose procedures. Should compliance be lower than expected, subjects will be counselled on dose administration. Patients will be re-admitted to the CRU for a second stay on Day 13. Subjects will receive their final dose on Day 14. They will be discharged on Day 15 (24 hours after intake of the last dose). Follow-up assessments will be on Day 28.

Patients who are not available for 2 in-clinic periods will be enrolled in the sub-cohort with sparse PK sampling. These patients will visit the CRU for ambulatory assessments on Day 1 in the morning (first dose) and on Days 7, 14, and 28, with follow-up assessments on Day 28. On Day 1 they will receive the first dose in the CRU. In addition, on Days 7 and 14 the patients will also receive their doses in the CRU. The remaining doses between Days 2-6 and

8-13 will be taken at home. Treatment compliance information will be collected while subject is dosing at-home via dosing diaries.

The planned multiple dose treatment in patients with moderate-to-severe psoriasis is provided in [Table 8](#). A total of 15 patients will be enrolled in one planned dose cohort. Subjects will be randomized to receive multiple oral doses of BMS-986251 or a matched placebo in a ratio of 4:1. The intended dosage form for patients is a tablet formulation, which is currently under development. The final selection of the dose will be made by the Sponsor's dose escalation review group and will be based on the safety, tolerability, PK and PD results of Part A and Part B.

Per protocol amendment the treatment duration may be extended to 12 weeks. Also per protocol amendment, Part C of this study may be extended with further cohorts, receiving lower repeated BMS-986251 dosed than the first cohort. A decision to extend the study with (a) lower-dosed cohort(s) will be based on the preliminary efficacy/safety balance of the 1st patient cohort. A high therapeutic response or, alternatively, poor safety or tolerability observed in the 1st patient cohort may be the basis to amend the study protocol for extension to a lower dosed cohort.

Table 8 IM024 005; Part C Dose Cohort

Cohort	Subjects (Active / Placebo)	Dose of BMS-986251	Duration	Fasted/Fed	Formulation
C1	12 / 3	60 mg QD	14 days	tbd	Oral tablet

QD = once daily; tbd = to be determined upon reviewed data

Dose may be adjusted based on data obtained in previous study parts.

